12.8 Grading of Laboratory Abnormalities

Clinical laboratory test results will be graded and used for dose escalation decisions and for analysis of safety at the end of the study. The laboratory values within the grading scale provided in the FDA guidance have been modified based on ICON Central Laboratories reference ranges. These values will be provided to the DEC.

Reference

Guidance for Industry titled "Toxicity Grading Scale for Healthy Adult and Adolescent Volunteers Enrolled in Preventive Vaccine Clinical Trials" issued by US Department of Health and Human Services Food and Drug Administration Center for Biologics Evaluation and Research on September 2007.

02 Dec 2019 Astellas Page 92 of 111

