6.2.1.2 Laboratory Values

Laboratory safety assessments will be collected at the screening visit and at study immunization if screening was performed > 7 days from study immunization [day 1]. Assessments will be repeated at follow-up visits on day 7 and day 30. These include the following:

- Hematology (hemoglobin, hematocrit, erythrocytes, leukocytes, differential WBC, platelets),
- Biochemistry (sodium, potassium, calcium, chloride, glucose, total cholesterol, triglycerides, blood urea nitrogen, creatinine, creatine kinase, uric acid, total protein, albumin, c-reactive protein),
- Coagulation profile (prothrombin time, activated partial thromboplastin time, fibrinogen)
- Hepatic profile (alkaline phosphatase, aspartate transaminase, alanine transaminase, γ -glutamyltransferase, total bilirubin, lactate dehydrogenase),
- Urinalysis (using dipstick - protein, glucose, pH, blood, leukocytes, urobilinogen, bilirubin, ketones, nitrite)
- Urine microscopy [optional] (casts, crystals, epithelial cells, leucocytes, erythrocytes, bacteria).
- Pregnancy Testing (Human Chorionic Gonadotropin (hCG))

Laboratory assessments assayed at baseline to determine eligibility are:

- Drug screening (amphetamines, barbiturates, benzodiazepines, cannabinoids and cocaine)
- Virology (Anti-HAV (IgM), HBsAG, Anti-HBc, Anti-HCV, Anti-HIV-1 and 2

Laboratory values collected on Days 7 and 30 will be categorized programmatically using the definitions in Appendix D: Grading Laboratory Abnormalities for Healthy Adult Subjects.

These post vaccination laboratory values are categorized into 4 grads of reactogenicity.

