7.5.3 Clinical Laboratory Evaluation

The baseline value is the last measurement taken prior to vaccine administration.

Quantitative clinical laboratory variables, i.e. hematology and biochemistry will be summarized using mean, standard deviation, minimum, maximum and median for each treatment group at each visit. Additionally, a within-subject change will be calculated as the post-baseline measurement minus the baseline measurement and summarized in the same way. Each laboratory result will be classified as low (L), normal (N), or high (H) at each visit according to the laboratory supplied reference ranges and laboratory data will be listed with flags for low or high.

Frequency tabulations of qualitative clinical laboratory variables (urinalysis) will be presented for treatment group (ASP3772 (1 μ g, 2 μ g, 5 μ g) or PCV13) and stage at each visit.

For hematology and biochemistry a summary of shifts (shift from normal or high to low, shift from normal or low to high) from baseline to worst finding during the treatment period will be presented for treatment group (ASP3772 (1 μ g, 2 μ g, 5 μ g) or PCV13) and stage.

The following data will be presented graphically by treatment group (ASP3772 (1 μ g, 2 μ g, 5 μ g) or PCV13) and stage:

- Box plot of Quantitative Laboratory Test Results will be displayed by treatment group (ASP3772 (1 μ g, 2 μ g, 5 μ g) or PCV13) and stage with PCV13 as a single group. The lower box will represent the 25th percentile, the middle line as the median, and the upper box the 75th percentile. A line showing the upper limit normal (ULN) and lower limit of normal (LLN) will be shown along with the minimum, maximum and outliers.
- Box plot of the maximum change from baseline for laboratory values will be displayed by treatment group (ASP3772 (1 μ g, 2 μ g, 5 μ g) or PCV13) and stage with PCV13 as a single group. A line showing the ULN and LLN will be shown. The lower box will be the 25th percentile, the upper box the 75th percentile, and the middle line the median. Minimum, maximum and outliers will be shown.

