7.5.3.1 Potentially Clinically Significant Laboratory Values

The frequency of Grades 1 through 4 hematology, biochemistry and urinalysis values and Grades 1 through 4 change from baseline as defined in the Guidance for Industry titled

“**Toxicity Grading Scale for Healthy Adult and Adolescent Volunteers Enrolled in Preventive Vaccine Clinical Trials**” (Appendix D) will be provided by treatment group (ASP3772 (1 μ g, 2 μ g, 5 μ g) or PCV13) and stage. Subjects treated with PCV13 will be combined into one group by stage.

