10.4 Appendix D: Grading Laboratory Abnormalities for Healthy Adult Subjects

Clinical laboratory test results will be graded and displayed using these grades. Grading values are based on ICON Central Laboratories, and will be adjusted if the reference ranges change.

Chemistry	ICON Reference range	Mild (Grade 1)	Moderate (Grade 2)	Severe (Grade 3)	Potentially Life-threatening (Grade 4)†
Sodium – Hyponatremia (mEq/L)	136-145*	133 – 135	131 – 132	126 – 130	< 126
Sodium – Hypernatremia (mEq/L)		146 – 147	148 – 149	150 – 151	> 151
Potassium – Hypokalemia (mEq/L)	3.5-5.1*	3.3 – 3.4	3.1 – 3.2	2.9 – 3.0	< 2.9
Potassium – Hyperkalemia (mEq/L)		5.2 – 5.3	5.4 – 5.5	5.6 – 5.7	> 5.7
Glucose – Hypoglycemia (mg/dL)		60 – 64	50 – 59	40 – 49	< 40
Glucose – Hyperglycemia	Fasting 74-99	100 – 110	111 – 125	> 125	Insulin requirements or hyperosmolar coma
Fasting (mg/dL)					
Random (mg/dL)	Random 74-139	140 – 155	156 – 230	> 230	
Blood Urea Nitrogen (mg/dL)	7-19 (F) [18-50] 10-20 (F) [>50] 9-21 (M) [18-50] 8-26 (M) [>50]	22 – 25	26 – 30	> 30	Requires dialysis
Creatinine (mg/dL)	0.55-1.02 (F) 0.72-1.18 (M)	1.5 – 1.7	1.8 – 2.1	2.2 – 2.5	> 2.5 or requires dialysis
Calcium – Hypocalcemia (mg/dL)	8.4-10.2	7.9 – 8.3	7.4 – 7.8	6.9 – 7.3	< 6.9
Calcium – Hypercalcemia (mg/dL)		10.3 – 11.0	11.1 – 11.5	11.6 – 12.0	> 12.0
Magnesium – Hypomagnesemia (mg/dL)	1.3-2.1*	1.1-1.2	0.9 – 1.0	0.7 – 0.8	< 0.7
Phosphorous – Hypophosphatemia (mg/dL)	2.3-4.7	2.0 – 2.2	1.7 – 1.9	1.3 – 1.6	< 1.3
Creatine Kinase (mg/dL)	29-168 (F) 30-200 (M)	1.25 – 1.5 × ULN***	1.6 – 3.0 × ULN	3.1 – 10 × ULN	> 10 × ULN
Albumin – Hypoalbuminemia (g/dL)	3.5-5.0 [18-61] 3.4-4.8 [>61]	2.8 – 3.1	2.5 – 2.7	< 2.5	NA
Total Protein – Hypoproteinemia (g/dL)	6.4-8.3	5.5 – 6.0	5.0 – 5.4	< 5.0	NA
ALP (Increase by Factor)	40-150	1.1 – 2.0 × ULN	2.1 – 3.0 × ULN	3.1 – 10 × ULN	> 10 × ULN
Liver Function Tests – ALT (Increase by Factor)	≤55	1.1 – 2.5 × ULN	2.6 – 5.0 × ULN	5.1 – 10 × ULN	> 10 × ULN
Liver Function Tests – AST (Increase by Factor)	5-34	1.1 – 2.5 × ULN	2.6 – 5.0 × ULN	5.1 – 10 × ULN	> 10 × ULN
Bilirubin – When Accompanied by Any Increase in Liver Function Test (Increase by Factor)	≤1.20	1.1 – 1.25 × ULN	1.26 – 1.5 × ULN	1.51 – 1.75 × ULN	> 1.75 × ULN
Bilirubin – When Liver Function Test is Normal (Increase by Factor)	≤1.20	1.1 – 1.5 × ULN	1.6 – 2.0 × ULN	2.0 – 3.0 × ULN	> 3.0 × ULN

Table continued on next page

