Chemistry	ICON Reference range	Mild (Grade 1)	Moderate (Grade 2)	Severe (Grade 3)	Potentially Life-threatening (Grade 4)†
Total Cholesterol (mg/dL)	Desirable: < 200 mg/dL Borderline: 200 – 239 mg/dL High: ≥ 240 mg/dL	201 – 210	211 – 225	> 226	NA

* The laboratory values provided in the tables serve as guidelines and are dependent upon institutional normal parameters. Institutional normal reference ranges should be provided to demonstrate that they are appropriate.

** The clinical signs or symptoms associated with laboratory abnormalities might result in characterization of the laboratory abnormalities as Potentially Life Threatening (Grade 4). For example, a low sodium value that falls within a grade 3 parameter (125-129 mE/L) should be recorded as a grade 4 hyponatremia event if the subject had a new seizure associated with the low sodium value.

***ULN" is the upper limit of the normal range.

ALP: alkaline phosphatase; ALT: alanine aminotransferase; AST: aspartate aminotransferase; NA: not applicable; ULN: upper limit of normal

Hematology	ICON Reference range	Mild (Grade 1)	Moderate (Grade 2)	Severe (Grade 3)	Potentially Life-threatening (Grade 4)
Hemoglobin (Female Subjects) (g/dL)	11.5-15.5	10.0 – 10.9	8.5 – 9.9	7.0 – 8.4	< 7.0
Hemoglobin (Female Subjects) Change From Baseline Value (g/dL)		Any decrease – 1.5	1.6 – 2.0	2.1 – 5.0	> 5.0
Hemoglobin (Male Subjects) (g/dL)	13.2-17.0	11.4 – 12.4	10.0 – 11.3	8.0 – 9.9	< 8.0
Hemoglobin (Male Subjects) Change From Baseline Value (g/dL)		Any decrease – 1.5	1.6 – 2.0	2.1 – 5.0	> 5.0
White Blood Cell Increase (k/uL)	3.50-11.10*	11 – 15	15.1 – 20	20.1 – 25	> 25
White Blood Cell Decrease (k/uL)	3.50-11.10*	2.5 – 3.5	1.5 – 2.4	1 – 1.4	< 1
Lymphocytes Decrease (k/uL)	1.2-4.0	0.5 - 0.6	0.3 - 0.4	0.1 - 0.2	< 0.1
Neutrophils Decrease (k/uL)	1.8-7.0	1.3 - 1.6	0.8 - 1.2	0.5 - 0.7	< 0.5
Eosinophils (k/uL)	0.0-0.5	0.8 – 1.2	1.3 - 5	> 5	Hypereosinophilic
Platelets Decreased (k/uL)	150-400	125 – 140	100 – 124	25 – 99	< 25
Prothrombin Time (Increase by Factor)	11.4-14.9 sec	1.01 – 1.10 × ULN†	1.11 – 1.20 × ULN	1.21 – 1.25 × ULN	> 1.25 ULN
Partial Thromboplastin Time (Increase by Factor)	24.7-34.4 sec	1.01 – 1.2 × ULN	1.21 – 1.4 × ULN	1.41 – 1.5 × ULN	> 1.5 × ULN
Fibrinogen Increase (mg/dL)	228-439	476 – 600	601 – 700	> 700	NA
Fibrinogen Decrease (mg/dL)		150 – 199	125 – 149	100 – 124	< 100 or associated with gross bleeding or DIC

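### Appendix D grades blood urea nitrogen of 22–26 mg/dL as Grade 1 or 2 in men over 50, although the same row gives 8–26 as their normal range

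*SAP*

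**What the plan says.** SAP Appendix D sets each laboratory grade beside the central laboratory's reference range. The BUN row gives 7–19 mg/dL for women aged 18–50 and 10–20 for women over 50; for men it gives "9-21 (M) [18-50] 8-26 (M) [>50" years. The grade columns do not split by sex or age: Grade 1 is 22–25, Grade 2 is 26–30, Grade 3 is above 30.

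The grades are meant to follow the laboratory. Protocol 12.8 states: "The laboratory values within the grading scale provided in the FDA guidance have been modified based on ICON Central Laboratories reference ranges". Appendix D adds: "Grading values are based on ICON Central Laboratories, and will be adjusted if the reference ranges change".

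Assignment is automatic. SAP 6.2.1.2: "Laboratory values collected on Days 7 and 30 will be categorized programmatically using the definitions in Appendix D", and then "These post vaccination laboratory values are categorized into 4 grads of reactogenicity". SAP 7.5.3.1 reports "The frequency of Grades 1 through 4 hematology, biochemistry and urinalysis values" by treatment group and stage. A separate classification in SAP 7.5.3 uses the ranges directly: "Each laboratory result will be classified as low (L), normal (N), or high (H) at each visit according to the laboratory supplied reference ranges".

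For total cholesterol, Appendix D quotes the laboratory's bands as "Desirable: < 200 mg/dL Borderline: 200 – 239 mg/dL High: ≥ 240 mg/dL" and sets Grade 1 at 201–210, Grade 2 at 211–225 and Grade 3 above 226.

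**The concern.** A single set of BUN bands cannot fit four different ranges, and here it conflicts outright with one of them. A 70-year-old man with a BUN of 24 on Day 7 is normal under SAP 7.5.3 and Grade 1 under SAP 7.5.3.1; at 26 he is normal and Grade 2. If his value was also 24 before vaccination he is still counted, because neither grading section conditions on baseline.

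Safety is the primary objective, and Protocol 12.8 says that the grades serve both dose-escalation review and the final safety analysis. The table of potentially clinically significant values would contain normal results, labelled as grades of reactogenicity, and would disagree with another safety table built from the same data.

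**Working it through.** **Inputs.** The BUN ranges and grade bands come from SAP Appendix D. Group 2 has 396 subjects aged 65–85 (SAP 3.2), so the over-50 range applies to every man in it. Stage 1 enrols ages 18–64, so the same range applies there from age 51.

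**Step 1: grade every whole-number value in each range.**

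| Sex and age | Range (mg/dL) | Whole-number values in range | In range but graded |
|---|---|---|---|
| Women 18–50 | 7–19 | 13 | none |
| Women >50 | 10–20 | 11 | none |
| Men 18–50 | 9–21 | 13 | none |
| Men >50 | 8–26 | 26 − 8 + 1 = 19 | 22, 23, 24, 25 (Grade 1); 26 (Grade 2) |

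The conflict is confined to men over 50: 5 of 19 values, of which only 26 is Grade 2. None reaches Grade 3. The bands are printed in whole numbers; a result reported between 25 and 26 would fall between them.

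**Step 2: where the cut-off of 22 fits.** The upper limit plus one unit is 20, 21, 22 and 27 for the four ranges in the order above. Only men aged 18–50 match. The same pattern reproduces the Grade 1 start for high sodium (145 + 1 = 146), potassium (5.1 + 0.1 = 5.2) and calcium (10.2 + 0.1 = 10.3). That the row was built from one range is an inference; the documents do not say so. The other rows with ranges split by sex or age (creatinine, creatine kinase, albumin, absolute hemoglobin) grade no in-range value.

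**Step 3: look for a safeguard.** SAP 6.2.1.2 and 7.5.3.1 contain no out-of-range or baseline condition. The Appendix D footnote calling the values guidelines is not marked on the BUN row. The promise to adjust applies only if ranges change, and this range is already printed there.

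**Step 4: size.** The documents give neither the sex split nor the BUN distribution. Assume 40–60% men, with 5–20% of them at 22–26:

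- low: 396 × 0.40 × 0.05 = 7.9
- high: 396 × 0.60 × 0.20 = 47.5

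That is about 8–48 Group 2 subjects, or about 2–12 in each group of 99 (99 × 0.40 × 0.05 = 2.0; 99 × 0.60 × 0.20 = 11.9).

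As a plausibility check, suppose 8–26 is the central 95% of values in men over 50. A normal shape has mean (8 + 26)/2 = 17 and SD (26 − 8)/(2 × 1.96) = 4.59, which puts 14.4% of men between 21.5 and 26.5; a lognormal shape gives 7.1%. Then 158.4 × 0.071 = 11 and 237.6 × 0.144 = 34 men per visit, inside the range above.

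**Step 5: cholesterol.** Grade 2 ends at 225 and Grade 3 is above 226, so exactly 226 has no grade. Values 227–239 are Grade 3 but lie in the laboratory's Borderline band.

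**The case against.** The best case for leaving the row alone is that little depends on it. BUN Grade 3 starts above 30, beyond every listed range, so the overlap cannot reach the Grade 3 laboratory stopping rule in Protocol 5.1.5, and no escalation criterion in Protocol 5.1.2 uses laboratory Grades 1–2. SAP 7.5.3.1 plans frequencies, not tests. The same bands apply in every arm. SAP 7.5.3 also shows ranges, flags, shifts and changes from baseline, where a BUN of 24 in an older man appears as normal. Under Protocol 5.5.1 a test abnormality becomes an adverse event only if it meets clinical criteria.

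All of this stands, and it limits the consequence to inflated Grade 1–2 counts and two tables that disagree. It does not make the row right. The investigator's review in Protocol 5.4.4 concerns out-of-range findings, so it would not remove an in-range value from the graded table.

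It is also fair that cholesterol is a different matter. Borderline is not normal, and no value in the Desirable band is graded. What remains is a gap at one value and a Grade 3 threshold that sits oddly beside the laboratory's bands.

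**Conclusion.** The BUN row contradicts itself for men over 50, and the planned programming carries the contradiction into the safety tables. The five-of-19 overlap follows from the row alone, taking whole-number reporting. The estimate of about 8–48 of 396 Group 2 subjects rests on assumed shares of men and of values at 22–26. Affected Stage 1 men aged 51–64 would add to it. Group 3 is outside the count, because the SAP 7.5.3.1 table names only ASP3772 and PCV13.

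Three stronger readings are not supported:

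- A reader might infer that raised values in women over 50 are missed, since 21 exceeds their limit of 20 but has no grade. Appendix D often starts grading beyond the limit (creatinine at 1.5 against 1.02 or 1.18; platelets at 140 against a lower limit of 150), and SAP 7.5.3 would still flag 21 as high.
- A reader might infer that a chance sex imbalance would look like a renal effect, as sex is not a stratification factor. With 5–20% of men affected, a 10-point imbalance moves the graded rate by 0.5–2.0 points, about 0.5–2 subjects per 99.
- A reader might infer that the phase 3 dose choice is at risk. Protocol 7.1 and SAP 4 tie that choice to Stage 2 responses, in text about OPA titers, not to renal grades.

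**What to change.** 1. The sponsor should reconcile the BUN grade bands with the reference range for men over 50 in the same row. The replacement limits are for the sponsor to set.
2. Add to SAP 6.2.1.2 a programming rule that a value inside the subject's own laboratory reference range is not graded. Limit it to absolute-value rows. Applied to change-from-baseline rows it would cancel the hemoglobin change grades, which can apply while the value is still in range: a man falling from 16.5 to 13.5 g/dL stays within 13.2–17.0, but a drop of 3.0 is Grade 3. The rule also removes the white-cell edge overlaps, where 11–11.10 and 3.5 are in range and Grade 1.
3. Do both. With the rule alone, the first graded value in a man over 50 would be 27, already Grade 2, and Grade 1 would be empty for him.
4. Separately, reconcile the cholesterol row: give 226 a grade and settle the Grade 3 threshold against the Borderline band. The rule in item 2 does not settle this, because the laboratory supplies bands there and not a normal range. Unlike the BUN overlap, this row touches Grade 3, which enters the stopping rule when considered related to immunization.

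The cost is two table rows, one programming rule, a footnote on the departure from the published scale, and consistent re-grading of cohorts that the dose escalation committee has already reviewed.

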3.2 Inclusion Criteria

A subject is eligible for the study if all of the following apply:

- 1. Institutional Review Board (IRB)/Independent Ethics Committee (IEC) approved written informed consent and privacy language as per national regulations (e.g., Health Insurance Portability and Accountability Act [HIPAA] Authorization for US sites) must be obtained from the subject prior to any study-related procedures (including withdrawal of prohibited medications, if applicable).
- 2. Stage 1: Subject is healthy male or female between 18 and 64 year of age inclusive, at screening.
- 3. Stage 2: Subject is a male or female between 65 and 85 years of age, inclusive, at screening who is healthy or has chronic controlled, stable disease with no change in disease severity, medical therapy and no hospitalization records in last 12 weeks as determined by medical history, physical examination and laboratory data and the clinical judgment of the Investigator.
- 4. A female subject is eligible to participate if she is not pregnant (see [Appendix 12.3 Contraception Requirements]) and at least 1 of the following conditions applies:
 - a. Not a woman of childbearing potential (WOCBP) as defined in [Appendix 12.3 Contraception Requirements]

OR

- b. WOCBP who agrees to follow the contraceptive guidance as defined in [Appendix 12.3 Contraception Requirements] at screening and for at least 28 days after the study vaccine administration.
- 5. Female subject must agree not to breastfeed starting at screening and for 28 days after the study vaccine administration.
- 6. Female subject must not donate ova starting at screening and for 28 days after the study vaccine administration
- 7. A male subject with female partner(s) of childbearing potential must agree to use contraception as detailed in [Appendix 12.3 Contraception Requirements] at screening and for at least 28 days after the study vaccine administration.
- 8. Male subject must not donate sperm starting at screening and for 90 days after the study vaccine administration

02 Dec 2019 Astellas Page 46 of 111

- 9. Male subject with a pregnant or breastfeeding partner(s) must agree to remain abstinent or use a condom for the duration of the pregnancy or time partner is breastfeeding at screening and for 28 after the study vaccine administration.
- 10. Subject agrees not to participate in another interventional study while participating in the present study.

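### Apart from hemoglobin, Appendix D laboratory grades ignore the baseline value, so stable pre-existing results in Stage 2 are tabulated as severe grades after vaccination

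*SAP*

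**What the plan says.** SAP 6.2.1.2 states: "Laboratory values collected on Days 7 and 30 will be categorized programmatically using the definitions in Appendix D". It then adds: "These post vaccination laboratory values are categorized into 4 grads of reactogenicity". SAP 7.5.3.1 plans to report "The frequency of Grades 1 through 4 hematology, biochemistry and urinalysis values and Grades 1 through 4 change from baseline", as defined in the cited toxicity guidance and Appendix D, by treatment group and stage. The table therefore covers Stage 2.

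Appendix D is headed as a scale for healthy adults. Its total cholesterol row gives the laboratory's own categories, "Borderline: 200 – 239 mg/dL High: ≥ 240 mg/dL", and beside them sets Grade 1 at 201–210, Grade 2 at 211–225 and Grade 3 above 226. Its hyperglycemia entry for Grade 4 is "Insulin requirements or hyperosmolar coma". The only rows expressed as a change from baseline are the two for hemoglobin, one per sex.

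Protocol 3.2 (criterion 3) admits a Stage 2 subject who is "healthy or has chronic controlled, stable disease with no change in disease severity". Protocol 3.3 names uncontrolled diabetes as an example of an excluded condition, and Protocol 5.1.3 keeps existing chronic medication at stable doses.

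For potentially clinically significant vital signs, SAP 7.5.4 requires both a change in grade from baseline and a numeric change consistent with Table C2.

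**The concern.** A grade reported after vaccination should tell the reader that something was found after vaccination that was not there before. For every analyte except hemoglobin, the planned table cannot show this. A severe grade that the subject brought into the study counts the same as one that arose after the injection.

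In healthy adults aged 18 to 64 this may matter little. In Stage 2 the population is elderly and may have controlled chronic disease, so out-of-range but stable results are to be expected. They would appear under a reactogenicity label in each Group 2 arm. The absolute rate of severe laboratory grades would be too high, and real changes in the affected analytes would have to be read against a background that does not come from the vaccine.

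SAP 6.2.1 lists laboratory assessments among the measures of the primary safety objective. Protocol 2.3 places them as additional safety assessments beside the primary endpoint bullets. Protocol 12.8 says the grades serve dose escalation and the end-of-study safety analysis.

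**Working it through.** The plan states no figure of its own on this point, so there is nothing to reproduce. The check applies the written bands.

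**1. Which rows use baseline.** Reading all of Appendix D (chemistry, hematology, urine), only the two hemoglobin change rows refer to baseline. The others use absolute values, multiples of the upper limit of normal, dipstick or count categories, or a clinical criterion.

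**2. The stable 230 example.** Baseline 230 and post-dose 230: since 230 > 226, the post-dose grade is 3. The change is 0, and the baseline grade would also be 3. The table counts one Grade 3. A rule requiring the post-dose grade to exceed the baseline grade counts none, because 3 is not greater than 3.

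**3. The borderline range against the grades.** There are 40 whole-number values from 200 to 239:

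| Values | Grade | Count |
|---|---|---|
| 201–210 | 1 | 10 |
| 211–225 | 2 | 15 |
| 227–239 | 3 | 13 |
| 200 and 226 | none | 2 |

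10 + 15 + 13 + 2 = 40. So 13 of the 40 values that the laboratory calls borderline are Grade 3. The value 226 falls between two bands and has no grade.

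**4. How many subjects.** Group sizes are from SAP 3.2: 99 per ASP3772 dose, and 3 × 33 = 99 pooled PCV13, so 3 × (99 + 33) = 396 in all. The documents give no cholesterol distribution, so the share p with a stable value above 226 is an assumption. The expected count is n × p.

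| Assumed p | Per 99 | Of 396 |
|---|---|---|
| 5% | 5.0 | 19.8 |
| 10% | 9.9 | 39.6 |
| 20% | 19.8 | 79.2 |
| 30% | 29.7 | 118.8 |

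As a guide to plausible p, assume a normal distribution with mean 180–200 and SD 35–45 (also not in the documents):
- Low end: z = (226 − 180)/35 = 1.31, upper tail 9%.
- High end: z = (226 − 200)/45 = 0.58, upper tail 28%.

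That is about 9 to 28 of 99.

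**5. Laboratory rule against vital signs rule.** SAP 7.5.4 makes a change in grade from baseline a condition for a clinically meaningful vital sign. SAP 7.5.3.1 sets no such condition for a graded laboratory value. The two rules differ, and the SAP gives no reason.

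**The case against.** **Baseline is not ignored altogether.** SAP 7.5.3 summarises within-subject change at each visit, plots the maximum change from baseline, and tabulates low/normal/high shifts. A stable 230 shows zero change and no shift there. Protocol 5.5.1.1 sends clinically significant laboratory findings not due to underlying disease to adverse event reporting, and exclusion 13 removes clinically significant screening abnormalities. All of this stands, and it limits the weight of the point. But none of these displays carries grades, so none separates a new Grade 3 from an old one. Nor need an investigator judge a cholesterol of 230 clinically significant.

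**The graded change from baseline in SAP 7.5.3.1 may mean all analytes.** The sentence can be read that way. It can also be read as hemoglobin only, since Appendix D defines no other change grades. The SAP should say which. On either reading the stable 230 stays at Grade 3 in the table of graded values.

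**Stronger readings that the documents do not support:**
- *Bias between arms.* PCV13 is randomised within each cohort, so the background is expected in all Group 2 arms.
- *Masking of a vaccine effect through lost power.* SAP 7.5.3.1 plans frequencies, with no test and no pooled endpoint of any Grade 3 laboratory result. Appendix D grades each analyte separately, so stable cholesterol cannot hide a rise in creatine kinase or a coagulation test.
- *Every established insulin user reported as Grade 4.* The Grade 4 wording is not limited to new use, but 6.2.1.2 grades laboratory values by program, and no rule links medication records to a grade. What would be output is unknown.
- *Triggering of the cohort stopping rule.* Protocol 5.1.5 requires that the laboratory abnormality be considered related to the immunization.

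**Conclusion.** The point holds as one of reporting and consistency. Outside hemoglobin, the graded laboratory table in SAP 7.5.3.1 counts pre-existing stable grades as post-vaccination grades. In Stage 2 this overstates the absolute severe-grade rate and adds noise for the affected analytes, in all Group 2 arms alike. That a stable 230 is Grade 3 follows from the text alone. The number of subjects rests on assumption: about 5 to 30 of 99 per group for an assumed 5% to 30% with stable cholesterol above 226. The partial baseline handling in 7.5.3 keeps this from being a serious defect. It is still worth correcting, because the table will be read as vaccine-related severity and the SAP already uses a baseline condition for vital signs.

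**What to change.** - In the SAP 7.5.3.1 tables, count a Day 7 or Day 30 laboratory grade as post-vaccination only if it is higher than the subject's own baseline grade.
- Add a table of baseline grade by worst post-dose grade, per analyte and arm. Read it against PCV13: the bands are narrow (225 to 227 mg/dL moves a subject from Grade 2 to Grade 3), so some upward moves will be ordinary variation.
- State whether the graded change from baseline in 7.5.3.1 covers hemoglobin only or all analytes.
- Keep the raw grade frequencies, without the reactogenicity label.
- Ask the sponsor to reconcile how the Grade 4 entry "Insulin requirements or hyperosmolar coma" is applied when grading is programmatic and Stage 2 can include controlled diabetes, and to settle the ungraded value 226. This asks only for clarification. It does not redefine a clinical grade or touch the escalation and stopping rules.

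The cost is SAP wording, one derived flag and one extra table. The baseline is already defined in SAP 7.5.3 and collected under Protocol 5.4.4, so no new assessment is needed.

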5.1.5 Criteria for Continuation of Immunization

Formal Stopping Rules for Individual Subjects:

Individual subjects will be discontinued from the study if:

- Subject is lost-to-follow-up despite reasonable efforts by the investigator to locate the subject.
- Subject voluntarily withdraws from the study at any time for any reason.

Formal Stopping Rules for Cohorts:

No additional subjects will be randomized or dosed in the study until the events below occurring in a subject who received ASP3772 are reviewed by the DEC and it is acceptable to resume cohort immunization.

- Unexplained death of a subject.
- Serious acute hypersensitivity reaction in a subject.
- One of the sentinel subjects experiences an AE of severe intensity related to ASP3772, when sentinel subjects are required.
- An SAE of the same character occurs in at least 2 subjects or 1 subject experiences a vaccine-related SAE.
- Grade 3 or higher lab abnormality considered related to the immunization occurs in 2 or more subjects [FDA Guidance for Industry, 2007].
- The same type of reactogenicity event assessed as Grade 3 or higher occurs in 2 or more subjects, or 1 of the sentinel subjects experiences a reactogenicity event assessed as Grade 3 or higher, using the FDA toxicity grading scale for preventative vaccines [FDA Guidance for Industry, 2007].
- An imbalance of unsolicited AEs between ASP3772 and PCV13 is observed.

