* The laboratory values provided in the tables serve as guidelines and are dependent upon institutional normal parameters. Institutional normal reference ranges should be provided to demonstrate that they are appropriate.

DIC: disseminated intravascular coagulation; NA: not applicable; ULN: upper limit of normal

† Upper limit of the normal range.

Urine	ICON Reference range	Mild (Grade 1)	Moderate (Grade 2)	Severe (Grade 3)	Potentially Life-threatening (Grade 4)
Protein	Negative	Trace	1+	2+	Hospitalization or dialysis
Glucose	Negative	Trace	1+	2+	Hospitalization for hyperglycemia
Blood (Microscopic) – RBC per HPF (rbc/hpf)	None	1 - 10	11 – 50	> 50 and/or gross blood	Hospitalization or packed RBC transfusion

RBC: red blood cell; HPF: high power field

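### SAP Appendix D gives some laboratory results no grade and one bilirubin value two grades, so programmed Grade 3+ counts may be misstated

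*SAP*

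**What the plan says.** SAP 6.2.1.2 states: "Laboratory values collected on Days 7 and 30 will be categorized programmatically using the definitions in Appendix D". SAP 7.5.3.1 then tabulates "The frequency of Grades 1 through 4 hematology, biochemistry and urinalysis values", together with graded changes from baseline. Protocol 12.8 gives the grades two uses: "Clinical laboratory test results will be graded and used for dose escalation decisions and for analysis of safety at the end of the study". Protocol 5.1.5 lists among its cohort pause criteria, for ASP3772 recipients, "Grade 3 or higher lab abnormality considered related to the immunization occurs in 2 or more subjects".

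The relevant rows of SAP 10.4 (Appendix D) are:

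- Urine protein, from reference range to Grade 4: "Protein Negative Trace 1+ 2+ Hospitalization or dialysis".
- Urine glucose, likewise: "Glucose Negative Trace 1+ 2+ Hospitalization for hyperglycemia".
- Total cholesterol: Grade 1 is 201-210, Grade 2 is 211-225, Grade 3 is > 226, and there is no Grade 4.
- Bilirubin with a normal liver test (ULN 1.20): Grade 2 is 1.6-2.0 and Grade 3 is 2.0-3.0 x ULN.
- ALT (ULN 55) and AST (ULN 34): Grade 2 is 2.6-5.0 and Grade 3 is 5.1-10 x ULN. The CK and prothrombin time rows have the same stepped form.
- Low sodium: Grade 3 is 126-130 and Grade 4 is < 126. A footnote example reads "a low sodium value that falls within a grade 3 parameter (125-129 mE/L) should be recorded as a grade 4 hyponatremia event", conditional on a new seizure.

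**The concern.** A program needs every abnormal result to map to exactly one grade, and a worse result never to a lower one. Appendix D fails this at identifiable values, some of them at the Grade 2/3 boundary, where the pause rule starts to count. In the urine rows the numerical scale stops at 2+, and Grade 4 is a clinical event. A 3+ dipstick in a subject without that event therefore matches no band and would leave the Grade 3+ count, although a 2+ result would be in it.

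Laboratory assessments are listed among the primary safety measures in SAP 6.2.1. Two programmers working from the same printed table could produce different Grade 3 frequencies.

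**Working it through.** The plan states no figure to reproduce. The check applies the printed bands literally and lists the values that match no grade or more than one.

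**1. Faults that depend on no rounding choice**

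- Urine protein and glucose: trace is Grade 1, 1+ is Grade 2, 2+ is Grade 3. A result of 3+ matches nothing unless the Grade 4 event occurred. That the laboratory reports categories above 2+ is an assumption; the documents do not list its categories.
- Cholesterol, as integers: 225 is Grade 2 and 227 is Grade 3. 226 is neither.
- Bilirubin, normal liver test: 2.0 x 1.20 = 2.40 satisfies both Grade 2 and Grade 3. This is the only double grade found.

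**2. Gaps between Grades 2 and 3 if the ratio is left unrounded** (assuming enzymes are reported as integers and PT to 0.1 s)

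| Test | ULN | Top of Grade 2 | Bottom of Grade 3 | No grade |
|---|---|---|---|---|
| ALT | 55 | 5.0 x 55 = 275 | 5.1 x 55 = 280.5 | 276-280 |
| AST | 34 | 5.0 x 34 = 170 | 5.1 x 34 = 173.4 | 171-173 |
| CK (men) | 200 | 3.0 x 200 = 600 | 3.1 x 200 = 620 | 601-619 |
| PT (s) | 14.9 | 1.20 x 14.9 = 17.88 | 1.21 x 14.9 = 18.03 | 17.9-18.0 |

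**3. Does one rounding rule close these gaps?**

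- One decimal closes the ALT gap (276/55 = 5.02, rounded to 5.0, Grade 2; 280/55 = 5.09, rounded to 5.1, Grade 3) but breaks PT. Values of 18.1-18.6 s have ratios 1.21-1.25, printed as Grade 3, and would round to 1.2, which is Grade 2. The next value, 18.7/14.9 = 1.26, rounds to 1.3, which is Grade 4. No PT could then be Grade 3.
- Two decimals closes the PT gap (17.9/14.9 = 1.20; 18.0/14.9 = 1.21) but leaves ALT 276-280 at 5.02-5.09, still ungraded.
- One decimal also widens the bilirubin overlap. Ratios from 1.95 to just under 2.05 become 2.0, which is 2.34-2.45 if results are reported to 0.01.

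The precision therefore has to be set row by row. Rounding does not touch urine above 2+ or cholesterol 226.

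**4. Sodium**

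| Value | Row | Footnote example |
|---|---|---|
| 125 | Grade 4 | within Grade 3 |
| 126-129 | Grade 3 | within Grade 3 |
| 130 | Grade 3 | outside Grade 3 |

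The row itself has no gap or overlap at integer values.

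**5. Size of the cholesterol gap**

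Assume normally distributed cholesterol with mean 180-200 and SD 35-45; none of these figures is in the documents. Then P(226) is about φ((226 − mean)/SD)/SD.

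- Lowest: mean 180, SD 35, giving 0.168/35 = 0.0048.
- Highest: mean 200, SD 35, giving 0.303/35 = 0.0087.

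Planned ASP3772 recipients in Stage 2 Group 2 supply 297 x 2 = 594 post-dose results, so about 594 x 0.0048 = 2.9 to 594 x 0.0087 = 5.2 would be exactly 226. Per dose cohort (99 x 2 = 198) that is about 1.0 to 1.7.

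**The case against.** The strongest reply is that little is lost. SAP 7.5.3 separately tabulates the qualitative urinalysis results, so a 3+ would appear there. SAP 7.5.3.2 counts ALT and AST above 3, 5, 10 and 20 x ULN, ALP above 1.5 x ULN and bilirubin above 2 x ULN. The pause rule needs relatedness and at least two subjects. Bands printed to one or two decimals suggest that ratios are meant to be rounded to that precision, and a rounding rule may stand in the separate TLF specifications. Laboratory grades are descriptive, and the same table applies to every arm.

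Most of this stands and limits the point. It does not remove the gaps that are independent of rounding. SAP 7.5.3.2 has no counterpart for CK, PT or cholesterol, and those other tables do not supply the grade on which the pause rule depends. Appendix D also calls its values guidelines, but in the chemistry and hematology tables the asterisk for that note sits on the sodium, potassium, magnesium and white-cell ranges, not on the rows at issue.

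A reader might infer that the sodium footnote makes the programmed grades wrong. The documents do not support that. The program works from the row, which is consistent, and the footnote illustrates a clinical upgrade. Only 125 and 130 differ, and 125 is Grade 3 or higher on either reading.

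**Conclusion.** The point holds in limited form. Appendix D leaves urine protein and glucose above 2+ and cholesterol 226 ungraded, and grades bilirubin 2.0 x ULN twice. The between-band gaps in the x ULN rows exist only if ratios are not rounded to each row's printed precision, which the SAP text does not specify. The sodium mismatch is an inconsistency to reconcile.

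A reader might go further and conclude that the Grade 3+ counts are wrong or that safety signals are lost. Neither follows. Counts are affected only if such values occur, and urinalysis categories and liver multiples are reported elsewhere. On the assumed distributions, cholesterol 226 would account for roughly 3 to 5 ASP3772 results in Stage 2. The urine effect cannot be sized without the laboratory's reporting categories. Correction is still worthwhile, because the table is run as code and Grade 3 is a decision threshold.

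**What to change.** Revise SAP Appendix D so that each row's bands are contiguous, non-overlapping and monotone, and a worse result is never graded lower than a milder one. In particular, a dipstick above 2+ must not be graded below 2+. State for each row the precision to which the result or its ratio to ULN is rounded before grading. Reconcile the sodium footnote (125-129) with the sodium row (126-130).

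Because Grade 3 feeds a pause rule, the sponsor should set the cut-points. Protocol 12.8 already provides grading values to the Dose Escalation Committee (DEC); keep those identical to the revised SAP table.

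The cost is appendix wording, grading code and a matching update of the DEC's values. A few results near boundaries may change grade.
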